## Principal Investigator: [name]

#### Abstract

Neonates and infants undergoing cardiac surgery are at high risk for perioperative bleeding and massive transfusion due to immature coagulation systems, cardiopulmonary bypass effects, hemodilution, and the complexity of surgeries. The current treatment for post-bypass bleeding includes transfusion of multiple rounds of blood products, which increases the risk of volume overload, immunologic burden, morbidity, and mortality. The average number of donor exposures for a neonate undergoing cardiac surgery requiring CBP at Children's Healthcare of Atlanta is nine exposures. Targeting transfusion strategies and alternative hemostatic agents that would reduce bleeding and transfusions would be a significant benefit to these patients.

The most common hemostatic derangement after CPB is an acute acquired hypofibrinogenemia, which compromises fibrin clot generation and platelet aggregation, resulting in increased bleeding and need for allogenic blood product transfusions. Currently, management of this acquired hypofibrinogenemia is replaced with a blood product, cryoprecipitate. Fibrinogen concentrate, RiaSTAP (CSL Bering), is a commercially available product that is being used off-label in cardiac and pediatric surgery to reduce bleeding and transfusions. However, a study specifically targeting neonates undergoing open-heart surgery with CPB has not been done to determine the efficacy of RiaSTAP in this population.

In this study, we plan to complete a multi-center randomized, control trial comparing cryoprecipitate to fibrinogen concentrate in reducing allogenic blood transfusions in infants undergoing cardiac surgery with CPB. Secondary outcomes will evaluate perioperative laboratory values, length of mechanical ventilation, length of ICU and hospital stays, as well as adverse events. Overall, we hope to use the results of this study to develop alternative transfusion strategies to treat post-CPB bleeding in infants.

### **Introduction and Background**

In patients undergoing open-heart surgery (OHS), transfusion of allogenic blood products is independently associated with increased morbidity and mortality (1,2). In response to this, research in adult cardiac anesthesia has focused on blood product usage and developing algorithms to limit blood product exposure. Due to the smaller population, considerable variability in patient characteristics, and wide range of procedures performed in pediatric cardiac patients, the literature regarding blood conservation strategies for pediatric cardiac patients is limited. In children undergoing OHS, there are no published algorithms even though product exposure, particularly in neonates, is significant. The National Heart, Lung and Blood Institute (NHLBI) has determined pediatric transfusion medicine (PTM) to be a high priority for clinical and translational research, specifically targeting transfusion strategies that could reduce short and long term morbidity and mortality (3).

Approximately 10,000 babies born with congenital heart disease require OHS during the first year of life. Excessive bleeding after CPB is an independent predictor of increased adverse events and massive transfusions in neonates (4). Higher perioperative transfusions of allogenic blood products during pediatric cardiac surgery are associated with increased mortality, increased pulmonary complications, prolonged mechanical ventilation, prolonged hospital stays, increased risk of hospital acquired infections and other adverse events (5,6). Many children with failed single-ventricle surgical palliation become higher-risk heart transplantation candidates because of the allo-sensitization after donor blood exposure. Finally, exposure to blood borne infections is a potential complication from receiving human derived blood products. Therefore, developing strategies to reduce bleeding and standardize blood transfusions for pediatric patients during CPB is an urgent need with a potential to reduce short and long-term morbidity and mortality.

Neonates and infants undergoing cardiac surgery are at high risk for perioperative bleeding and massive transfusion due to immature coagulation systems, cardiopulmonary bypass (CPB) effects (deep hypothermia, extreme hemodilution, large nonendothelialized surfaces) and complexity of surgery. The most common hemostatic derangement after CPB is an acute acquired hypofibrinogenemia, which compromises fibrin clot generation and platelet aggregation, resulting in increased bleeding and need for allogenic blood product transfusions. Recent studies suggest that qualitative and quantitative fibrinogen deficiencies may contribute to impaired hemostasis in neonates and infants (7). Using confocal microscopy, Brown et al demonstrated neonatal clot formation before and after cardiopulmonary bypass is more porous and less dense than clots from adults. However, the addition of adult fibrinogen was able to establish more effective clot formation in neonates (7). In conjunction with the decreased function of neonatal fibrinogen, the acute acquired hypofibrinogenemia after OHS contributes to impaired fibrin clot generation and platelet aggregation. Currently, fresh frozen plasma and cryoprecipitate are used to supplement fibrinogen in pediatric cardiac patients, thus increasing the allogenic transfusion exposures.

RiaSTAP (fibrinogen concentrate (FC)), an FDA-approved medication for congenital hypofibrinogenemia, is being used off-label for treatment of acute acquired hypofibrinogenemia associated with massive bleeding and CPB in adult and pediatric patients (8-10). Fibrinogen concentrate has many potential advantages for pediatric patients including 1) smaller volume to achieve target levels of fibrinogen, 2) decreased exposure to allogenic blood products, 3) decreased risk of infectious transmission, immunologic or allergic reactions, and 4) no required cross-matching or thawing process that makes it rapidly available for all patients. Recent studies found that FC was as effective as cryoprecipitate in reducing bleeding and transfusions for pediatric patients undergoing craniofacial and open-heart surgery (9,10). However, these studies did not specifically examine the neonatal and infant population, who are most vulnerable to the affects of hypofibrinogenemia, excessive bleeding and large transfusions associated with

OHS. We propose that FC poses many advantages over current options, but there is a clear need for a randomized, prospective study in this population. After communication with the Center for Biologic Evaluation and Research (CBER) and the Office of Blood Research and Review (OBRR) at the FDA, an IND exemption was granted for this study. A grant from The Child Health Research Institute at Stanford University and SPARK has supported the initial work on this study and will help support the center at Children's Healthcare of Atlanta.

#### **Significance:**

#### Specific Aim #1:

Demonstrate that fibrinogen concentrate can reduce allogenic donor exposures when compared with cryoprecipitate in infants undergoing cardiac surgery with CPB. The most common cause of post-bypass coagulopathy in infants after bypass surgery is from an acquired hypofibrinogenemia due to hemodilution from the bypass circuit. Secondly, immature neonatal fibringen does not function as well as adult fibringen in forming stable clots. This acquired hypofibrinogenemia is currently treated with cryoprecipitate, a human derived blood product, which requires blood type matching and time to obtain from the blood bank. The FDA has approved fibrinogen concentrate, a lyophilized protein with minimal side effects, for use in pediatric and adult patients with congenital hypofibrinogenemia. Fibrinogen concentrate is being used off-label for treatment of acute acquired hypofibrinogenemia associated with massive bleeding and CPB in pediatric patients. No studies have been done specifically in cardiac surgery patients <12 months, who are most at risk for hypofibrinogenemia due to their small circulating blood volumes, immature coagulation systems, and potential long-term effects of transfusion related risks. Therefore, we have received an IND exemption from the FDA to conduct this randomized, control trial comparing fibrinogen concentrate to cryoprecipitate in hemostatic management of post-bypass coagulopathy in patients <12 months. We propose that replacing cryoprecipitate with reconstituted fibrinogen concentrate will be as effective as cryoprecipitate in treating post-CPB bleeding and decrease total donor exposures by 20%.

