### Study Population:

The following criteria will be used to determine patient eligibility: Inclusion Criteria:

- Full term neonates (32-42 weeks gestational age)
- weight  $\geq$  to 3 kg at time of surgery
- Infants less than 12 months of age
- Infants and Neonates undergoing elective cardiac surgery requiring CPB at Children's Healthcare of Atlanta or Lucile Packard Children's Hospital at Stanford Hospital
- No known patient or family history of coagulation defect or coagulopathy
- Parents willing to participate and able to understand and sign the provided informed consent

Exclusion Criteria:

- Preterm neonates (less than 32 weeks gestation)
- Patients less than 3 kg at time of surgery
- Patients >12 months of age
- Patients undergoing emergent procedure
- Patients undergoing cardiac surgery not requiring CPB
- Patients with known coagulation defect or coagulopathy
- Family history of coagulation defect or coagulopathy
- Parents unwilling to participate or unable to understand and sign the provided informed consent

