## Sample Size/Statistical Analysis

The primary aim of this study is to determine if fibrinogen concentrate can decrease allogenic donor transfusions in infants undergoing cardiac surgery with cardiopulmonary bypass in patients when compared with the current standard of care, cryoprecipitate. Therefore, we analyzed our blood product transfusion data from CHOA in infants requiring CPB. We counted the number of units of packed red blood cells (PRBCs), fresh frozen plasma (FFP), cryoprecipitate, and platelets the patient received. Each unit was counted as one donor exposure. On average, the patients had nine donor exposures. We propose replacing two units of cryoprecipitate with fibrinogen concentrate will result in a 20% reduction in donor exposures. In order to achieve a power of 0.9, we plan to enroll 15 patients in each arm, for 30 patients at this institution.

The Quantitative Statistical Unit at Stanford University will provide assistance with data management, conducting data analyses, and interpreting statistical results. Continuous variables will be compared by analysis of variance and will be presented as mean  $\pm$  standard variation if normally distributed or by median (IQ range) if non-normally distributed. Nominal variables will be compared by chi-squared analysis or Fisher's exact test. Significance will be defined as a p-value less than or equal to 0.05.

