In secondary analyses, we used a Mann-Whitney U test to test whether the secondary outcomes measured continuously differed by arm. For categorical secondary outcomes, we used a Chi-squared test when the expected count in each cell was > 5, otherwise we used a Fisher's exact test. All secondary analyses were conducted on the subset of PP patients. Sensitivity analyses were performed for the secondary outcomes adjusting for site, complexity, weight, and CPB time. For continuous outcomes, we log-transformed the secondary outcomes then fit a linear regression model and for the outcome of any AE, we fit a logistic regression model.

Sample Size Justification: We designed our study to have 90% power to detect a reduction of two allogenic blood product transfusions when assuming that the mean number of units in patients receiving cryoprecipitate was 7 with a standard deviation of 2.2 units in both arms. Using a two-sample t-test and performing a two-sided test with an alpha = 0.05 we found that 27 patients per arm were needed. We assumed approximately 10% of patients would be missing their primary outcome and enrolled 30 patients per arm.

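### The 90% power applies to a two-unit reduction (29% of the SAP's mean of 7), not to the 20% reduction stated in Aim 1 and beside power 0.9 in the protocol

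*Protocol*

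**What the plan says.** **Protocol, Significance, Specific Aim #1.** The hypothesis is that replacing cryoprecipitate with fibrinogen concentrate will "decrease total donor exposures by 20" per cent. No absolute number of units and no power are given there.

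**Protocol, Sample Size/Statistical Analysis.** The baseline comes from one site's records: "we analyzed our blood product transfusion data from CHOA in infants requiring CPB". Each unit of red cells, plasma, cryoprecipitate or platelets counts as one exposure, and "On average, the patients had nine donor exposures". No time window is given for the count. The effect is then set out as "replacing two units of cryoprecipitate with fibrinogen concentrate will result in a 20% reduction in donor exposures", and the next sentence attaches a power of 0.9 to 15 patients per arm at that institution. No standard deviation is stated.

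**Protocol, Abstract.** The same nine appears with a neonate label: "The average number of donor exposures for a neonate undergoing cardiac surgery requiring CBP".

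**SAP, Sample Size Justification.** The trial has 90% power for a two-unit reduction, "assuming that the mean number of units in patients receiving cryoprecipitate was 7 with a standard deviation of 2.2 units in both arms". The test is a two-sided two-sample t-test at alpha 0.05. The result is 27 per arm, raised to 30 per arm for about 10% missing primary outcomes.

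**SAP, Statistical Analysis for Primary outcome.** The outcome is total intraoperative units. The SAP does not mention the 20% or say why the planning mean is 7 rather than 9.

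**The concern.** The primary aim is expressed only as a percentage, and the current power statement only as an absolute number of units. The two agree, after rounding, when the baseline is nine. They part when the baseline becomes seven, and the percentage was not updated. Someone who reads Aim 1 beside the stated 90% will conclude that the trial had 90% power for a 20% reduction. On the SAP's SD and number per arm it did not, whichever baseline is used.

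The mismatch also affects how the result is read. The SAP reports an adjusted ITT difference of 1.61 units. Divided by nine that is 18%, below the 20% of Aim 1. Divided by seven it is 23%, above it. Neither figure estimates the relative reduction in the trial, since both denominators are planning assumptions. They show only that the 20% cannot serve as a benchmark until its baseline is stated.

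**Working it through.** **Inputs**

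- Relative target 20%: Protocol, Specific Aim #1 and Sample Size/Statistical Analysis.
- Baseline 9 and two units replaced: Protocol, Sample Size/Statistical Analysis.
- Control mean 7, SD 2.2 in both arms, reduction of two units, two-sided alpha 0.05, 27 evaluable and 30 enrolled per arm: SAP, Sample Size Justification.

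**Step 1. Reproduce the SAP's figure.** For n per arm, the two-sample t-test has 2n − 2 degrees of freedom and noncentrality

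λ = δ / (σ √(2/n)).

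With δ = 2, σ = 2.2, n = 27: 2.2 × √(2/27) = 0.599, so λ = 2/0.599 = 3.34 on 52 degrees of freedom. Power is 90.6%. The smallest n that reaches 90% is 27, and 27/0.9 = 30. The SAP's calculation is correct.

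**Step 2. Relate units to percentages.**

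- Two units: 2/9 = 22.2% and 2/7 = 28.6%.
- Twenty per cent: 0.20 × 9 = 1.8 units and 0.20 × 7 = 1.4 units.

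**Step 3. Power for each effect, same formula, SD 2.2.** At n = 27, λ is 1.4/0.599 = 2.34 and 1.8/0.599 = 3.01. At n = 30 the divisor is 2.2 × √(2/30) = 0.568.

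| Effect | Units | Power, 27 per arm | Power, 30 per arm |
|---|---|---|---|
| 20% of 7 | 1.4 | 63% | 68% |
| 20% of 9 | 1.8 | 84% | 88% |
| SAP effect | 2.0 | 91% | 93% |

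**Step 4. Scale of the gap.** At SD 2.2, 90% power would take 53 evaluable per arm for 1.4 units (53/0.9, so 59 enrolled) and 33 for 1.8 units (33/0.9, so 37 enrolled). These numbers show size only and are not a proposal.

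**Step 5. The protocol's own 0.9.** It cannot be reproduced, because no SD is given. At 15 per arm, 90% power would need an SD of about 1.6 for two units or about 1.5 for 1.8 units. With the SAP's SD of 2.2, 15 per arm gives 67% for two units. For the full trial, the SAP's calculation is the one that can be checked.

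**The case against.** The strongest reply is that the absolute effect never changed. The protocol starts from two units of cryoprecipitate, and its 20% is a rounded description of 2/9. The SAP powers for the same two units. On that view nobody set a target of 1.4 units. It appears only when a percentage derived from nine is applied to seven. On the protocol's own baseline, 20% is 1.8 units, and power is 84% to 88%, not far short of 90%.

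Most of this stands. The SAP's sample size is right for the effect it names, and 1.4 units should not be presented as the trial's target. What remains is that Aim 1 states only the percentage, the protocol sets that percentage beside 0.9, and the stated power is not reached for a literal 20% on either baseline at SD 2.2 with the planned 27 evaluable per arm or with all 30.

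Three stronger readings are tempting, and the documents do not support them.

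- *The 9 and the 7 describe different populations.* The abstract says neonate, the sample-size section says infants, and eligibility includes "Infants less than 12 months of age". But the protocol uses the two words loosely, and its consent section calls the trial child a neonate. Aim 1 speaks of total donor exposures and the SAP of intraoperative units, so the time window could explain the gap. If it does, 20% of 7 is not a like-for-like quantity either. Nor do the documents show that nine is unusable for infants under 12 months.
- *The observed control median shows that the baseline was wrong.* The SAP reports an ITT control median of 5 units. A median cannot be set directly against a planned mean, and an outcome does not show what was reasonable to assume at planning.
- *The trial was too small.* For its stated two-unit effect it was not.

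**Conclusion.** The point holds as a mismatch between a stated target and a stated power. The 90% belongs to an absolute reduction of two units, about 29% of the SAP's assumed mean of 7. It does not belong to a 20% reduction, for which power at 27 per arm is about 63% on a baseline of 7 and about 84% on a baseline of 9.

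These figures assume that the SAP's SD of 2.2 holds at each effect size and baseline, and they use the SAP's unadjusted t-test. The primary analysis adjusts for institution and complexity of surgery. That could raise power somewhat, but the documents give no figure for the gain. The 63% also assumes that the 20% may be carried over to the SAP's intraoperative mean, which the documents do not settle.

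The change from 9 to 7 is unexplained. The consequence is for interpretation and reporting. The sample size, the test and the validity of the primary comparison are unaffected.

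**What to change.** Add a dated clarification to the SAP, cross-referenced from Aim 1 and from the protocol's sample-size section, that says:

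1. The powered effect is an absolute reduction of two units in the SAP's primary outcome, about 29% of the assumed control mean of 7. The 90% power is not attached to the 20% figure.
2. With SD 2.2 and 27 evaluable per arm, power for a 20% reduction is about 63% on a mean of 7 (1.4 units) and about 84% on a mean of 9 (1.8 units).
3. For both 9 and 7: the population, the time window (total or intraoperative), and the reason for the change.

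The SAP already reports results, so the 20% hypothesis should stay visible as written. Replacing it with 29% now, without a note, would look like a hypothesis revised after the outcome was known.

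The cost is a short text change and a look back at the source of the two baselines. The stated power for the 20% target becomes less favourable. Enrolment and the primary analysis stay as they are.

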### Specific Aim #2:

Comparison of fibrinogen concentrate to cryoprecipitate as a safe and effective hemostatic agent:

By evaluating the laboratory values, transfusion requirements, and outcomes, we will examine the effectiveness of FC in reducing transfusion related risks, such as 1) length of mechanical ventilation time, 2) length of ICU stay, 3) length of hospital stay, 4) adverse events within seven days of surgery, 5) preoperative and post-operative coagulation laboratory values.

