Repurposing of Fibrinogen Concentrate as a Cost-Effective and Safe Hemostatic Agent in Infants Undergoing Cardiac Surgery on Cardiopulmonary Bypass

Statistical Analysis Plan

NCT03014700

March 8, 2019

[name], Principal Investigator Emory University

[name], Principal Investigator Stanford University

Intention-to-Treat (ITT) Analysis Set

The ITT Analysis Set consists of all enrolled subjects. Efficacy summarization and analysis will be conducted using the ITT analysis set.

Per Protocol Analysis Set (PPAS):

The subset of subjects in the full analysis (ITT) set who complied with the protocol sufficiently (see below) without any major protocol deviations. Confirmatory analysis was performed using the PPAS dataset. Final definition of PPAS were defined prior to data lock. Elements of PPAS may include exclusion criteria such as:

- Violation of inclusion or exclusion criteria
- Did not receive study medication
- Did not go on cardiac bypass during surgical intervention
- Patients unable to wean from bypass in operating room

Statistical Analysis for Primary outcome (using ITT):

The primary analysis followed the ITT principle and was performed using a linear regression adjusted for the randomization strata of institution and complexity of surgery. PP analysis was also performed for the primary outcome of total units of intraoperative allogenic blood transfusions.

Results for Primary outcome:

Patients in the FC group received significantly fewer total units of allogenic blood transfusions when compared to patients in the cryoprecipitate group (5 units [IQR 4.00,7.00] in the ITT analysis and 6 units [IQR 5.00,7.00] in the PP analysis in the control group, and 4 units [IQR 3.00,5.00] in the ITT analysis and 4 units [IQR 3.00,5.00] in the PP analysis in the study group). In the ITT analysis, the FC group received a mean of 1.61 [95% CI 0.3-2.91, p-value =0.02] less allogenic donor exposures than the cryoprecipitate group when adjusted for institution and complexity. In a PP analysis, the FC group received a mean of 2.67 [95% CI 1.75-3.59, p-value <0.001] less allogenic donor exposures than the cryoprecipitate group when adjusted for institution and complexity.

Statistical Analysis for Secondary Outcomes (using Per Protocol population)

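### The planned adverse-event comparison is a difference test with no interval or margin, so it cannot answer the safety part of Aim 2

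*Protocol*

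**What the plan says.** **The objective.** The heading of Specific Aim #2 in the protocol reads "Comparison of fibrinogen concentrate to cryoprecipitate as a safe and effective hemostatic agent". The SAP is titled "Repurposing of Fibrinogen Concentrate as a Cost-Effective and Safe Hemostatic Agent in Infants Undergoing Cardiac Surgery on Cardiopulmonary Bypass". Under the Aim 2 heading, the protocol lists "adverse events within seven days of surgery" among the outcomes. The text there, and in the second Aim 2 section under Experimental Design and Methods, presents these outcomes as transfusion-related risks that FC may reduce. That second section names infection and thrombosis.

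**The analysis.** The protocol (Sample Size/Statistical Analysis) says "Nominal variables will be compared by chi-squared analysis or Fisher's exact test" and "Significance will be defined as a p-value less than or equal to 0.05". For categorical secondary outcomes the SAP says "we used a Chi-squared test when the expected count in each cell was > 5, otherwise we used a Fisher's exact test". It adds a sensitivity analysis adjusted for site, complexity, weight and bypass time: "for the outcome of any AE, we fit a logistic regression model". All secondary analyses use the per-protocol subset.

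**Oversight.** The Adverse Events Reporting and Data Safety Monitoring Plan sections provide case-by-case review by the investigators and quarterly review by anesthesiologists outside the study. They state no rule for comparing the arms.

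**Sample size.** The SAP's 90% power applies to transfused units only. Neither document gives an expected adverse-event rate, an acceptable excess or a safety power calculation.

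**The concern.** A difference test takes equal risk as its null hypothesis. A small p-value is evidence of a difference; a large one means only that a difference was not detected. The plan names comparative safety as an aim but supplies no quantity that would support or refute it.

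This matters most for uncommon events. Thrombosis is named in the protocol as a product risk, and with about 30 infants per arm a substantial excess could easily give p > 0.05. If such a result were then described as FC being as safe as cryoprecipitate, the smaller the trial and the rarer the event, the more easily the product would pass. The concern is with the adverse-event conclusion, not with the hemostasis comparison.

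**Working it through.** **1. The plan's own figure.** SAP inputs: difference 2 units, SD 2.2, two-sided α = 0.05, power 90%.

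Normal approximation: n = 2(1.960 + 1.282)² × 2.2² / 2² = 25.4, so 26 per arm. The t-test solution is 26.4, so 27 per arm. Allowing for 10% missing: 27 / 0.90 = 30 per arm. The SAP's 27 and 30 reproduce. Adverse events play no part in this calculation.

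**2. Chance of missing a doubled event rate.** The documents give no rates, so the control rate p is an assumption and the FC rate is set to 2p. The SAP rule was applied to every possible 2×2 table: chi-squared if all expected counts exceed 5, otherwise Fisher. The chi-squared test is taken as uncorrected and the p ≤ 0.05 threshold as two-sided; neither is stated for these tests. Then

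miss rate = 1 − Σ Bin(a; n, p) × Bin(b; n, 2p), summed over tables with p-value ≤ 0.05.

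| Assumed control → FC rate | Missed, 30 per arm | Missed, 27 per arm |
|---|---|---|
| 5% → 10% | 98% | 99% |
| 10% → 20% | 89% | 91% |
| 15% → 30% | 74% | 76% |
| 20% → 40% | 61% | 63% |
| 25% → 50% | 48% | 52% |
| 30% → 60% | 34% | 41% |
| 40% → 80% | 10% | 13% |

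The 27 comes from the SAP's allowance for missing primary outcomes, not from the adverse-event analysis set. The per-protocol set may be smaller: at 25 per arm, 20% → 40% is missed 66% of the time.

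**3. What remains possible when the arms look the same.** With x events out of n in each arm, the observed difference is zero. If the Wilson 95% limits for x/n are l and u, the Newcombe upper limit for FC minus cryoprecipitate is √[(u − x/n)² + (x/n − l)²].

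For 3/30 in each arm: l = 0.0346, u = 0.2562, giving √[0.1562² + 0.0654²] = 0.169.

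| Events per arm, of 30 | Excess not excluded |
|---|---|
| 0 | 11 points |
| 3 | 17 points |
| 6 | 20 points |
| 12 | 23 points |

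At 12/30 the event is common enough for a doubling usually to be detected. Identical observed counts would still leave an excess of 23 points open.

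**The case against.** The strongest reply is that the text under the Aim 2 heading asks whether FC *reduces* transfusion-related risks, adverse events among them. A difference test suits that question, and a non-significant result would simply mean that no reduction was shown. On this view, safety is a word in a heading and a title. The point about the wording stands, and it limits the concern: the tests fit the reduction question. They do not fit the safety question that the heading and the title also raise.

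A reader might infer that the plan will take p > 0.05 as proof of safety. No sentence in either document says so. What is missing is a criterion; no wrong rule is stated.

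A reader might also infer that the significance test is the whole of the safety assessment, or that it misses a doubling at least 60% of the time. Neither inference is supported. There is an adjusted logistic model, and there is case-by-case and quarterly review, though none of these sets a between-arm criterion. The 60% figure holds only for control rates up to about 20%. The one adverse-event outcome named in the SAP's models is the composite of any event, and its rate could be higher.

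Finally, low power for adverse events is usual in a 60-patient trial sized on another endpoint. That is true, and the remedy is to show the uncertainty rather than enlarge the trial.

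**Conclusion.** The concern holds in limited form. The plan puts safety relative to cryoprecipitate into an aim and a title, but its between-arm adverse-event analyses are difference tests with no interval, margin or supporting power. As written, they cannot support a conclusion of safety.

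The size depends on event rates that the documents do not give. For events with a control rate of 10% or less, a doubling is missed about nine times in ten or more. For a common composite at 30–40%, it is missed 10–41% of the time across 27 and 30 per arm. The interval result does not require an assumed true rate, only the observed counts: equal counts at 30 per arm leave an excess of roughly 11 to 23 points unexcluded. The calculations assume two-sided tests, uncorrected chi-squared and arms of 27 or 30. This should be changed before any safety statement is made.

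**What to change.** In the SAP's section on secondary outcomes, report the FC-minus-cryoprecipitate risk difference with a two-sided 95% confidence interval for any adverse event and for each adverse event reported by arm. Use Newcombe's method, or an exact method where counts are sparse. Base any safety statement on the upper limit, by saying how large an excess is excluded and that a smaller one is not. State that p > 0.05 will not be reported as showing FC to be safe or comparable. In the protocol, reword the safety part of Aim 2 as estimating the difference in adverse-event risk.

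This does not create a prespecified margin. The SAP already reports primary results, so a margin chosen now would not be prespecified; estimation is the honest alternative.

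The cost is some rewording and a few lines of code, with no new patients or data. The downside is a weaker safety claim, with intervals of roughly 11 to 23 points either side of zero in plain view when the arms have equal counts.
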